MK-2206 is the first allosteric AKT inhibitor to enter clinical development. As an AKT inhibitor, it is equally potent towards purified recombinant human AKT1 and AKT2 isoenzymes, and 5-fold less potent against AKT3 (Investigator's Brochure, 2008). It has an advantage of having a higher intrinsic selectivity for AKT compared to the active-site AKT-specific inhibitors, i.e., ATP-competitive AKT inhibitors which have been clinically evaluated thus far. *In vitro* and *in vivo* anticancer efficacy of MK-2206 was demonstrated in breast cancer cell lines and in the A2780 ovarian cancer xenograft model in nude mouse and rat, either as a single agent or in combination with erlotinib, trastuzumab, and docetaxel.

Preclinical safety assessment studies in the most sensitive species, dogs, demonstrated NOAEL (no observed adverse effect level) at a 2.5 mg/kg dose (Cmax of 365 nM and AUC0-48h of 8.52  $\mu$ M·h) and NOEL for cardiovascular effects at a 1 mg/kg dose (Cmax of 92 nM and AUC0-48h of 1.59  $\mu$ M. Based on these data, the human equivalent doses are 34 mg (NOEL) and 80 mg (NOAEL) for a 60-kg man.

The projected human clearance for MK-2206 is 2-4 mL/min/kg with bioavailability in the range of 50%-75%. Although preclinical safety/tolerability studies identified health risks of prolonged QTc interval and hyperglycemia associated with MK-2206, no significant hyperglycemia has been seen thus far on the phase I trial; and while Grades 1-2 QTc prolongation has been noted with MK-2206 in clinical trials, it has not been thought to be clinically significant.

Merck is completing a phase 1 clinical trial with MK-2206 as a single agent in patients with solid tumors. Preliminary data from this study suggest that the dosing regimen of 60 mg orally (PO) every other day (QOD) is well-tolerated and achieves target effects of AKT inhibition. In addition, Merck has completed Phase I testing of a weekly schedule of MK-2206 and has recommended a Phase II dose of 200 mg orally (PO) weekly. Pharmacokinetic data is available for this weekly regimen. This schedule has demonstrated less toxicity than the 60 mg PO QOD schedule, appears to have at least equal antitumor activity, and is favored by Merck for subsequent trials.

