## **5.9 Protocol Evaluation**

5.9.1 Prior to each treatment cycle (please refer to Section **5.3** for definition of a cycle):

5.9.1.1 SOAP progress note.

5.9.1.2 Laboratory examination:

5.9.1.2.1 Hematological Profile: CBC with differential and platelet count.

5.9.1.2.2 Biochemical Profile: Sodium, potassium, chloride, CO2, BUN, creatinine, glucose, AST, ALT, alkaline phosphatase, bilirubin, albumin, total protein, LDH, calcium, phosphorous and magnesium.

5.9.1.3 Vital signs including weight.

5.9.2 Restaging and Imaging:

Restaging will be performed at the end of every two cycles, +/- 1 week, as defined for each treatment arm. Therefore, restaging will be performed every 6 weeks +/- 1 week for the Erlotinib, AZD6244, and Lapatinib arms; every 8 weeks +/- 1 week for the MK-2206 arm, and every 12 weeks +/- 1 week for the Sunitinib arm. Imaging modalities will consist of CT or MRI, as appropriate for disease evaluation. The use of FDG-PET will be allowed but it would be considered exploratory and its results will not be used for treatment decisions.

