## **6 DOSING DELAYS/DOSE MODIFICATIONS**

Patients enrolled in one of the experimental study arms may continue to receive additional cycles of therapy provided that the patient meets the following criteria on Day 1 of each cycle:

- ANC > 1,000/mcL
- Platelets > 100,000/mcL
- Non-hematologic toxicity recovered to < grade 2 (or tolerable grade 2 or baseline)
- No evidence of progressive disease

In the event of an adverse event at least possibly related to the agent, the doses of such agent should be adjusted according to the guidelines shown in the Dose Delays / Dose Modifications tables shown below (Sections 6.1 and 6.2). If an adverse event is not covered in such tables, doses may be reduced or held at the discretion of the investigator for the subject's safety.

Subjects with adverse events that are manageable with supportive therapy may not require dose reductions (e.g., nausea/vomiting ~~may~~ be treated with antiemetics, diarrhea may be treated with loperamide, and electrolyte ~~abnormalities~~ may be corrected with supplements rather than by dose reduction).

Subjects will be withdrawn from the study arm if they fail to recover to CTC Grade 0-1 or tolerable grade 2 (or within 1 grade of starting values for pre-existing laboratory abnormalities) from a treatment-related adverse event within 21 days OR they experience agent related adverse events requiring dose modification despite two previous dose reductions (i.e. would require a 3rd dose reduction) unless the investigator and CTEP monitor agree that the subject should remain in the study arm because of evidence that the patient is/may continue deriving benefit from continuing study treatment (i.e. patient has PR, CR, SD > 3 months). The appropriate reduced dose will be determined after discussion between the principal investigator and CTEP monitor.

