### 6.1.2 MK2206

**Table 10:** MK2206 Monotherapy Dose Level Reductions

Dose Level	MK2206 Dose
Starting Dose	200 mg QW
First Dose Reduction	135 mg QW
Second Dose Reduction	90 mg QW

**Table 11:** Dosage Modification Criteria for MK2206-related Toxicities

Event	AE Grade or Observation	Dose modification
Dermatology/Skin	Grade 1 or 2	Maintain dose
	Grade 3 or 4 or intolerable grade 2	Hold MK2206 until < tolerable grade 2, then reduce 1 dose level and resume treatment  .
	Recurrent Grade 3	Hold MK2206 until < tolerable grade 2, then reduce 1 additional dose level and resume treatment  .
	Recurrent Grade 3 after 2 dose reductions	Remove patient from study arm.
	Grade 4	Patients with grade 4 rash (i.e. life threatening generalized exfoliative ulceration; erythema

		multiforme/toxic epidermal necrolysis should be removed from study arm.
Diarrhea  (if anti-diarrheal treatment is ineffective)	Grade 1 or 2	Maintain dose; continue anti-diarrheal treatment. Loperamide (4 mg at first onset, followed by 2 mg every 2–4 hrs until diarrhea free for 12 hrs)
	Grade 3 or 4	Hold MK2206 until < tolerable grade 2, loperamide; reduce 1 dose level and resume treatment  .
	Recurrent Grade 3 or 4	Hold MK2206 until < tolerable grade 2, loperamide; reduce 1 additional dose level and resume treatment  .
	Recurrent Grade 3 or 4 after 2 dose reductions	Remove patient from study arm.
Hematologic  (neutrophils, platelets, hemoglobin)	Grade 1 or 2	Maintain dose
	Grade 3 or 4	Hold MK2206 until < grade 2, then reduce 1 dose level and resume treatment.
	Recurrent Grade 3 or 4	Hold MK2206 until < grade 2, then reduce 1 additional dose level and resume treatment.
	Recurrent Grade 3 or 4 after 2 dose reductions	Remove patient from study arm.
Liver Function  (serum bilirubin, AST, or ALT)	Grade 1 or 2	Maintain dose
	Grade 3 or 4	Hold MK2206 until < grade 2, then reduce 1 dose level and resume treatment
	Recurrent Grade 3 or 4	Hold MK2206 until < grade 2, then reduce 1 additional dose level and resume treatment
	Recurrent Grade 3 or 4 after 2 dose reductions	Remove patient from study arm.
Other non-hematological toxicity	Grade 1 or 2	Maintain dose
	Any Grade 2 of concern (e.g., prolonged cardiac, pulmonary, or neurotoxicity, intolerable stomatitis)	Hold MK2206 until < grade 1, then reduce 1 dose level and resume treatment
	Grade 3 or 4	Hold MK2206 until < tolerable grade 2, then reduce 1 dose level and resume treatment 

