	Recurrent	Hold MK2206 until < tolerable grade 2, then reduce 1 additional dose level and resume

	Grade 3 or 4	treatment 
1	If event has not improved to < tolerable grade 2 or baseline within < 21 days, patient should be removed from the study.	
2	Patients with medically concerning grade 3 or 4 AEs related to MK2206 may be taken off study at investigator's discretion.	

In the event of Grade 3 hyperglycemic events (>250 mg/dL) consult with an endocrinologist or other specialist. If glucose levels do not return to grade 1 or lower within one week of appropriate therapy, patients should be considered to have a DLT (dose modification, etc.). Appropriate therapy will usually involve oral antihyperglycemic agents, since the inhibition of glucose transport into the cell by AKT/mTOR inhibitors may render insulin ineffective. The goal of therapy is to keep fasting glucose <150 mg/dL, random blood glucose levels <180 mg/dL, and Hemoglobin A1c <8%. Glucose monitoring should be performed weekly, during the first cycle of therapy, and on day 1 of subsequent cycles, prior to drug administration. Hemoglobin A1c monitoring, for patients requiring treatment of hyperglycemia, should be performed with each cycle of MK-2206 therapy.

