## 12 STUDY CALENDAR

Baseline evaluations are to be conducted within 1 week prior to start of protocol therapy. Scans and x-rays must be done <4 weeks prior to the start of therapy. In the event that the patient's condition is deteriorating, laboratory evaluations should be repeated within 48 hours prior to initiation of the next cycle of therapy. The study calendar does not apply to individuals enrolled for EGFR germline mutation testing only; please refer to Section 5.6 for testing and follow-up of these individuals.

	Screening – Part 1 Molecular Profiling and Correlative Studies	Screening – Part 2 Treatment Arm Eligibility (see Section 3.3)	Treatment Cycles (see Section 5.3; clinic visits may be extended to every 6 weeks for the Erlotinib, AZD6244, and Lapatinib arms; every 8 weeks for the MK-2206 arm; and every 12 weeks for the Sunitinib arm)	Off treatment
Biopsy for molecular profiling 	X		Upon disease progression per section 5 (optional)	
Targeted therapies 			See section 5 for details regarding agent administration and scheduling	
Informed consent	X		N/A	
Demographics	X			
NOS arm data 		X		
Medical history 		X	Every clinic visit	X
Concurrent Meds 		X	Every clinic visit	X
NIH Advance Directives Form 	X			
Physical exam 		X	Every clinic visit	X
Vital signs 		X	Every clinic visit	X
Height 		X	N/A	
Weight 		X	Every clinic visit	X
Performance status 		X	Every clinic visit	X
CBC w/diff, plts 		X	Prior to each clinic visit	X
Serum chemistry 		X	Prior to each clinic visit	X
PT, aPTT 		X		X
Urinalysis 		X		X
EKG 		X	As clinically indicated	X
BP 			Weekly during cycle 1	
ECHO/MUGA 		X	Every other treatment cycle	
Adverse event evaluation 			X-----X	X
Tumor measurements 		X	Approximately every 6, 8, or 12 weeks, as defined for each treatment arm. See Section 5.8.2 for details. Documentation (radiologic) must be provided for patients removed from study arm for progressive disease.	X

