Grade 1/grade 2 prolongation of QTc-interval was observed in 14 out of 64 patients (21.9%) with available 12-lead ECG data. Prolongations  $\geq 30$  msec but  $< 60$  msec occurred in 4 of these patients. Grade 3 QTc prolongation was reported in one patient who received 135 mg QW. Episodes of QTc interval prolongation were in general isolated with no apparent dependency on dose or exposure levels, and were not considered clinically significant by investigators and were not reported as adverse experiences. Eleven patients experienced sinus bradycardia ( $< 50$  bpm) during Holter or ECG monitoring. These events were asymptomatic and were not clinically significant. While a causal relationship between these events and administration of MK-2206 is uncertain, similar side effects were seen preclinically in conscious dogs. Consequently, patients with a history or current evidence of heart disease should be excluded from enrollment on MK-2206 trials. Standard 12-lead ECG measurements should be performed at the protocol-specified time-points.

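### The MK-2206 arm omits the heart-disease exclusion its own background advises, and silent QTc prolongation can go unseen during dosing

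*Combined protocol and SAP*

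**What the plan says.** **Background.** Section 2.1.4 names two preclinical risks: "Although preclinical safety/tolerability studies identified health risks of prolonged QTc interval and hyperglycemia associated with MK-2206". Appendix A (18.1.1.1, Clinical Toxicology) reports QTc findings in patients, advises that "patients with a history or current evidence of heart disease should be excluded from enrollment on MK-2206 trials", and leaves the ECG time-points to the protocol.

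**Screening.** Section 3.3.3.2 lists prior AKT inhibitor therapy, allergy to similar compounds, and a note that hyperglycaemia must be controlled. It has no cardiac item. Two general criteria apply to all treatment arms. Section 3.2.2.5 excludes uncontrolled illness, with examples that include symptomatic NYHA class III or IV heart failure, unstable angina and arrhythmia. Section 3.2.2.6 excludes a QTc of 500 msec or more and other significant ECG abnormalities.

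**During dosing.** In the Section 12 calendar, the EKG row is marked at screening and off treatment; under treatment cycles it reads "As clinically indicated". The pre-cycle list in Section 5.9.1 has a progress note, laboratory tests and "Vital signs including weight", but no ECG. Glucose has a timetable in Section 6.1.2: "Glucose monitoring should be performed weekly, during the first cycle of therapy, and on day 1 of subsequent cycles, prior to drug administration".

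**Rules that reach QTc.** Table 11 has no QTc row. Its row for other non-haematological toxicity covers "Any Grade 2 of concern (e.g., prolonged cardiac, pulmonary, or neurotoxicity, intolerable stomatitis" and, at grade 3 or 4, says "Hold MK2206 until < tolerable grade 2, then reduce 1 dose level and resume treatment". Section 6 requires on day 1 of each cycle: "Non-hematologic toxicity recovered to < grade 2 (or tolerable grade 2 or baseline".

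**The concern.** There are two gaps. First, the background's advice on whom to exclude is carried into the arm only in part, through general criteria aimed at unstable disease. Someone with stable angina, a coronary stent or an old infarct can enter if nothing is uncontrolled and the ECG shows no significant abnormality.

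Second, QTc prolongation often has no symptoms, and a rule triggered by its grade depends on an ECG having been taken. With none scheduled between first and last dose, a patient could reach the level at which Table 11 holds the drug and still receive the next weekly dose.

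The safety of a small number of patients is at stake, and so is how the results will be read. If few QTc events are reported from an arm in which QTc was not systematically measured, the count could be mistaken for evidence of cardiac safety.

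**Working it through.** **1. Reproduce the plan's figure.** Appendix A gives grade 1 or 2 QTc prolongation in 14 of 64 patients with ECG data: 14/64 = 0.21875, or 21.9% as stated. The same text says the episodes were not reported as adverse experiences. The figure is a rate of ECG findings, so it shows that such changes can be invisible without an ECG. It is not an adverse-event rate and is not used as one here.

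**2. Set the advice beside the screen.**

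| Source | Cardiac patients kept out of MK-2206 |
|---|---|
| Appendix A (advice) | any history or current evidence of heart disease |
| 3.2.2.5 (all arms) | uncontrolled illness, such as class III or IV heart failure, unstable angina, arrhythmia |
| 3.2.2.6 (all arms) | QTc of 500 msec or more; other significant ECG abnormalities |
| 3.3.3.2 (this arm) | none |

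What the advice covers and the criteria do not is stable heart disease with an acceptable ECG.

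**3. Count what is scheduled.** Dosing is weekly in 28-day cycles (Section 5.7.1.3 and the Appendix B diary), and restaging is every 8 weeks (Section 5.9.2).
- Doses by first restaging: 2 cycles × 4 = 8. Doses in 26 weeks: 26.
- Scheduled ECGs between first and last dose: 0 in both periods.
- Clinic visits are every 4 weeks and may be extended to every 8 (Section 5.3).

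**4. Trace the rules.** The Table 11 hold and the day 1 recovery check both turn on the grade of the toxicity. For QTc, the grade during dosing is known only if an ECG was ordered as clinically indicated. The off-treatment EKG comes after dosing, so it can lead to a report but not to a hold. Section 7.4 also does not require grade 1 events to be collected.

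**5. Cost of a wider exclusion.** The documents do not give the share of otherwise eligible patients with a cardiac history. Assume f between 10% and 30%. Patients needed to fill n places = n/(1 − f), rounded up:
- first stage, n = 9: 9/0.9 = 10; 9/0.7 = 12.9, so 13;
- full stratum, n = 20: 20/0.9 = 22.2, so 23; 20/0.7 = 28.6, so 29.

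**The case against.** The case for leaving the plan alone has real weight.

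- **The clinical signal is soft.** Appendix A describes the QTc episodes as generally isolated, without apparent dependence on dose or exposure and not clinically significant. It calls the causal link of the ECG and bradycardia findings uncertain. That supports light monitoring. It does not explain why the exclusion advice in the same passage was only partly adopted.
- **A screen and a safety net exist.** The general criteria remove the highest-risk patients, Section 3.2.2.7 asks for efforts to replace QT-prolonging drugs, and Section 16.2 speaks of excluding symptomatic heart failure from class II. Clinically indicated ECGs include those prompted by concern about QTc, and electrolytes are checked before cycles. So it would be wrong to infer that the hold rules cannot operate; they can miss silent prolongation.
- **No instruction on ECG timing is breached.** The background leaves the time-points to the protocol, which chose screening and off treatment for all arms.
- **Glucose is not a fair yardstick.** Hyperglycaemia was seen in about 76% of patients on alternate-day dosing, so closer monitoring of it is proportionate.

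A reader might also infer that MK-2206 is handled more loosely than sunitinib although its QTc listing is in a more frequent category. The documents do not support that. Appendix A gives sunitinib's stricter rules their own origin: dose-dependent QT prolongation, reported Torsade de Pointes and an NCI action letter. Table 16 continues sunitinib at the current dose between 450 and 550 msec. The 500 msec entry limit applies to every arm.

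**Conclusion.** The point holds and is minor. Stable heart disease is admitted to the MK-2206 arm against the background's advice, and no ECG is scheduled during dosing, so silent QTc prolongation at the hold level can be missed. The two-stage design and the response analysis are not affected.

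The number of patients concerned cannot be estimated. A reader might build a rate from the single grade 3 case reported at 135 mg weekly, but its denominator is not stated; one event over an assumed denominator gives an interval too wide to inform anything. Nor does that case show a dose effect, since the background sees none in patients.

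Importance is lowered further because Section 16.4 says the treatment arms closed on 3/22/2016 and the study stays open for molecular profiling only. The documents do not show that any patient is still receiving MK-2206. The reporting consequence remains. The conclusion assumes that the calendar and Section 5.9.1 are the full schedule, and that no separate site instruction required on-treatment ECGs.

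**What to change.** 1. **Section 3.3.3.2:** add the Appendix A exclusion for a history or current evidence of heart disease, or a dated list in the format of 3.3.5.2.4. The cost is a smaller eligible pool: 10 to 13 otherwise eligible patients for a first stage of 9, and 23 to 29 for a full stratum of 20, under the assumed 10% to 30% prevalence.

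2. **Sections 5.9.1 and 12, for any further dosing:** a 12-lead ECG at the existing day 1 clinic visit of each later cycle would be reasonable. Over 26 weeks (6.5 cycles) that is 6 ECGs on the 4-weekly schedule and 3 if visits are extended to every 8 weeks. Taken before that day's dose, it shows trough rather than peak effect. Post-dose or day 22 ECGs would need clinic time or visits that are not now scheduled, and they are not required. A separate 500 msec rule is not required either, since it would largely duplicate the grade 3 hold.

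3. **Study report:** state how many MK-2206 patients had an ECG between first and last dose, and that QTc was not systematically assessed, so that few QTc events are not read as evidence of cardiac safety. This costs one count and a sentence or two, and it is the part that still matters now that the arms are closed.

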#### *Developmental/Reproductive Toxicity*

Developmental and reproductive toxicity studies of MK-2206 have not been performed thus far. MK-2206 was not tested in pregnant or breast-feeding women. Women of child-bearing potential and men participating in clinical studies of MK-2206 must use appropriate contraception, including abstinence and double-barrier methods, throughout MK-2206 therapy. In preclinical mutagenicity studies, MK-2206 was neither genotoxic or mutagenic.

#### *Drug Interactions*

No clinical drug interaction studies have been performed with MK-2206. Oxidative metabolism of MK-2206 in human liver microsomes was catalyzed primarily by CYP3A4. MK-2206 was not an inhibitor of the major CYPs. MK-2206 was shown to be a P-gp substrate.

#### *Weekly dosing*

Preclinical studies in animal models have shown evidence of improved efficacy of the once weekly (QW) dosing in mono-therapy using the A2780 xenograft (PTEN mutant) model in two independent studies. Additionally, QW dosing of MK-2206 results in similar or enhanced single agent and combination efficacy in NCI-H-292 Xenografts. In the phase I clinical trial PN002, MK-2206 showed a Cmax = 170 nM (after 1st dose) and Cmax = 225 nM (SS), which could potentially lead to better tumor penetration, more tumor cytotoxicity and better efficacy in comparison to the every other day (QOD) mode of administration. Mean Coverage above target PK was 133 hours (out of 168 hours), which may potentially alleviate skin toxicity. Furthermore, this dosing schedule is significantly more convenient for the patient. More detailed information and updates about the rationale for the use of QW dosing can be found in the investigational brochure.

#### **16.1.1.2 AZD6244**

AZD6244 (ARRY-142886) is a potent, selective, orally-available, and non-ATP competitive small molecule inhibitor of the mitogen-activated protein (MAP) kinase kinase, MEK-1/2 (Investigator's Brochure, 2009; Friday and Adjei, 2008). AZD6244 inhibited the activity of purified MEK enzyme with an IC50 of 10-14 nM, and was found to be inactive or only

minimally active at 10  $\mu$ M against a panel of other kinases, including epidermal growth factor receptor (EGFR), ERB2, p38 $\alpha$ , ERK2, and MKK 6 kinases. Because ERK is the only known substrate of MEK, the inhibition of MEK will target only the ERK signal transduction pathway and other signal transduction pathways will not be blocked. AZD6244 is metabolized to biologically active N-desmethyl AZD6244 which is more potent than the parent compound. In vitro, in vivo and preliminary results from clinical studies suggest that AZD6244 exhibits a favorable pharmacologic and toxicologic profile.

The RAS/RAF/MEK/ERK signaling pathway plays a central role in the regulation of many cellular processes including proliferation, survival, differentiation, apoptosis, motility, and metabolism (O'Neill and Kolch, 2004; Wellbrock et al., 2004). This pathway is one of the most important and best understood MAP kinase signal transduction pathways, activated by a diverse group of extracellular signals including integrins, growth factor receptors (i.e., EGFR, platelet-derived growth factor receptor [PDGFR], and insulin-like growth factor-1 receptor), and cytokines (Janssen et al., 2005). Activated RAS triggers the phosphorylation and activation of RAF kinase which then phosphorylates MEK1 and MEK2 on 2 serine residues (Ahn et al., 2001). Activated MEK phosphorylates its only known substrates, ERK1 and ERK2. Phosphorylated ERK dimerizes and translocates to the nucleus (Khokhlatchev et al., 1998) where it is involved in several important cellular functions, including cell proliferation.

Overexpression of growth factors or growth factor receptors involved in the RAS/RAF/MEK/ERK pathway and activating genetic mutations of the signaling proteins may lead to uncontrolled proliferation and tumor formation. For example, RAS genes are the most frequently mutated oncogenes detected in human tumors (Janssen et al., 2005). RAS proteins are guanine nucleotide binding proteins that activate RAF proteins when bound to GTP. Cancer-associated mutations in RAS proteins stabilize the GTP-bound form of RAS, thereby providing a constitutive signal downstream in the cascade. In addition to being found in almost all pancreatic adenocarcinomas, RAS mutations are found in ~50% of colorectal carcinomas, 25-50% of lung adenocarcinomas, and also in some breast or ovarian cancers. BRAF mutations have also been observed in many human cancers, particularly melanoma (30-60%), thyroid (30-50%), colorectal (5-20%), and ovarian (~30%) cancers (Wellbrock et al., 2004; Friday et al., 2008). These mutations in BRAF usually involve gain-of-function substitutions that render the kinases constitutively active. Also, studies of primary tumor samples and cell lines have shown constitutive activation or overactivation of the MAP kinase pathways in cancers of the pancreas, colon, lung, ovary, and kidney (Hoshino et al., 1999). Therefore, agents targeting the RAS/RAF/MEK/ERK pathway may inhibit oncogenic signaling in tumor cells.

